4.3 Study Patients

4.3.1 Disposition of Patients

Patient disposition will be summarized for all enrolled patients by dosing regimen and over all patients combined. Summaries will include the number and percentage of patients in each analysis set as well as the number and percentage of patients discontinuing the treatment or study by the primary reason for discontinuation.

4.3.2 Protocol Deviations

Important protocol deviations will be summarized by dosing regimen and over all patients combined for the Full Analysis Set. Important protocol deviations are protocol deviations captured on study that are deemed by the Sponsor to potentially impact the safety or efficacy conclusions of the study.

Any important protocol deviations will be determined and appropriately categorized prior to database lock. The number and percentage of patients with any important protocol deviations as well as the number and percentage of patients with deviations within each category will be presented. Corresponding patient listings will be provided.

4.4 Demographic and Other Baseline Characteristics

Demographic and baseline characteristics will be summarized for the Safety Analysis Population, Full Analysis Set, and modified Intent-to-Treat Population by dosing regimen and over all patients combined.

Demographic variables include age as collected on the eCRF, age category (<65 or ≥ 65 years), sex at birth, childbearing potential (if female), ethnicity, and race. Age will be summarized using descriptive statistics. Sex, ethnicity, and race will be summarized with the number and percentage of patients in each parameter category.

Baseline characteristics include height, weight, body mass index (BMI), medical history, ECOG performance status, primary cancer diagnosis at study entry, time since initial primary cancer diagnosis, stage of disease at study entry, histology, and number of prior systemic therapies. Body mass index will be calculated as: weight (kg) / [height (cm) / 100]².

Height, weight, and BMI at baseline will be summarized using descriptive statistics. ECOG performance status will be summarized with the number and percentage of patients in each category.

Medical history conditions will be mapped to preferred terms and system organ classes using the Medical Dictionary for Regulatory Activities (MedDRA, version 27.1).

Frequency counts and percentages to summarize patients reporting abnormal medical history by system organ class will be presented.

For primary cancer history, diagnosis when patient entered the study (RM-NPC, Not NPC [gastric cancer, lymphoepithelioma-like carcinoma, leiomyosarcoma, etc.]), stage at study entry, histology, and number of prior systemic therapies will be summarized with the number and percentage of patients in each category. The time since the date of original primary cancer diagnosis will be summarized using descriptive statistics. All other primary cancer history will be included in patient data listings.

4.5 Efficacy Evaluation

4.5.1 Datasets Analyzed

Efficacy summaries will be produced as described in [Section 4.2](#). Efficacy summaries will be repeated for the modified Intent-to-Treat Population (if meaningfully different than the Full Analysis Set) as supportive evidence and to assess the robustness of efficacy findings. A data listing of patients excluded from the Full Analysis Set and modified Intent-to-Treat Population, to include the reason for exclusion, will be presented.

4.5.2 Measurements of Treatment Compliance

Compliance with both nanatinostat and valganciclovir will be determined as the total number of tablets taken divided by the expected number of tablets taken, multiplied by 100.

The expected number of tablets administered will be determined using the prescribed dosing information contained in Table 4 of the clinical study protocol, where nanatinostat and valganciclovir are dispensed in 10 mg and 450 mg tablets, respectively. The number of tablets expected will be calculated for each cycle and then multiplied by the number of cycles the patient completes.

The total number of tablets taken will be determined using the data recorded on the Study Drug Exposure eCRF pages for nanatinostat and valganciclovir. If a patient is administered study drug as expected (with no changes to dose administered, no interruptions, delays, or missed doses), then the Study Drug Exposure eCRFs will include a record for that cycle that indicates “No Change to Dose.” In this case, the total number of tablets taken in each cycle will be calculated as the number of days in the cycle where the doses were administered (multiplied by two if a divided dose). Missed doses are recorded on the Study Drug Exposure eCRFs as “Missed/Dosing Error.” When calculating the number of missed doses, if a patient reports “Missed/Dosing Error” on the eCRF, it will be assumed no study drug was administered on that date.

Compliance with pembrolizumab will be determined as the total number of infusions received divided by the number of expected infusions, multiplied by 100. The number of expected infusions will be determined using the dosing schedule provided in Figure 10 of the clinical study protocol. The total number of infusions received will be determined using the *Study Drug Administration Log - Pembrolizumab* eCRF.

Dosing compliance will be summarized using descriptive statistics, for each dosing regimen based on the Safety Analysis Population. The number and percentages of patients who are <80% compliant and $\geq 80\%$ compliant within each dosing regimen will be summarized. Treatment compliance will also be included in a by-patient data listing.

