5.6. Dose Modification Guidelines for Study Treatment-Related Toxicities

Nanatinostat and Valganciclovir

For patients who do not tolerate the protocol-specified dosing schedule or develop toxicities, dose adjustments of nanatinostat and valganciclovir are permitted. Dose adjustments, except for valganciclovir adjustments based on renal function (Section 5.6.2), must be approved by the Medical Monitor or Sponsor prior to implementing. These changes must be accurately recorded in the eCRFs.

Given the expectation that both study drugs are required for activity, both agents will be held and restarted in parallel. Dose modification guidelines in case of study treatment-related toxicity for nanatinostat, valganciclovir, and pembrolizumab are presented in Table 7.

Unless otherwise indicated in Table 7, any AE that requires a dose hold should resolve to Grade 1 or baseline generally within 14 days before resuming treatment at the current or a reduced dose.

The management of patients requiring more than 2 dose reductions should be discussed with the Sponsor's Medical Monitor.

For patients in Phase 2 treated with nanatinostat and valganciclovir in combination with pembrolizumab, if pembrolizumab treatment is discontinued, nanatinostat and valganciclovir dosing may continue. If nanatinostat or valganciclovir are discontinued, the Sponsor's Medical Monitor should be consulted about pembrolizumab treatment.

Pembrolizumab

Dose reduction of pembrolizumab will not be required in this study. For the management of specific immune-mediated adverse reactions, see Table 8. Otherwise, withhold pembrolizumab for severe (Grade 3) immune-mediated adverse reactions and permanently discontinue pembrolizumab for those that are life-threatening (Grade 4), recurrent Grade 3 that require systemic immunosuppressive treatment, or if not able to reduce corticosteroid dosing to 10 mg per day or less of prednisone or an equivalent within 12 weeks of initiating steroids.

If a patient requires a dose interruption of >6 weeks of pembrolizumab from the intended day of the next scheduled dose, pembrolizumab should be discontinued.

Exceptions following a discussion between the Sponsor's Medical Monitor and the Investigator may be possible. Reasons for a potential exception include, but are not limited to, the following:

- 1. Dosing delays to allow for prolonged steroid tapers to manage drug-related AEs.

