5.6.2. Dose Modifications for Patients with Renal Impairment

Patients who develop an elevated creatinine while on study should have their dose of valganciclovir adjusted per Table 9.

An estimated creatinine clearance in adults is calculated from serum creatinine by the following formulas:

For serum creatinine measured in mg/dL:

For males =
$$(140 - age [years]) \times (body weight [kg]) = XX mL/min$$

(72) × (serum creatinine [mg/dL])

For females =
$$(140 - age [years]) \times (body weight [kg]) = XX mL/min \times 0.85$$

(72) × (serum creatinine [mg/dL])

For serum creatinine measured in µmol/L:

For males =
$$(140 - age [years]) \times (body weight [kg]) \times 1.23 = XX mL/min$$

Serum creatinine (μ mol/L)

For females =
$$(140 - age [years]) \times (body weight [kg]) \times 1.23 = XX mL/min \times 0.85$$

Serum creatinine (µmol/L)

For patients already receiving a dose of valganciclovir lower than that recommended in Table 9, the Investigator should discuss the amount of dose reduction with the Sponsor's Medical Monitor.

Creatinine Clearance (mL/minute)	Valganciclovir Dose (daily)	Valganciclovir Dose (twice daily)
≥60	900 mg once daily	900 mg twice daily
40–59	450 mg once daily	450 mg twice daily
25–39	450 mg every 2 days	450 mg once daily
10–24	450 mg twice weekly	450 mg every 2 days
<10 (on hemodialysis)	Not recommended (discuss with Medical Monitor)	Not recommended (discuss with Medical Monitor)

 Table 9:
 Valganciclovir Dose Adjustments for Patients with Renal Impairment

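### The SAP's compliance denominator ignores directed in-cycle holds, valganciclovir doses outside Table 4 and unfinished cycles, so patients who followed instructions can score below 80%, above 100%, or have no value

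*SAP*

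**What the plan says.** SAP 4.5.2 defines compliance with each oral drug as 100 times tablets taken over tablets expected. On the denominator it says: "The expected number of tablets administered will be determined using the prescribed dosing information contained in Table 4 of the clinical study protocol". It continues: "The number of tablets expected will be calculated for each cycle and then multiplied by the number of cycles the patient completes". There is no reference to the protocol's dose-modification tables and no rule for a cycle that is started but not finished.

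On the numerator it says: "The total number of tablets taken will be determined using the data recorded on the Study Drug Exposure eCRF pages". This is not limited to completed cycles. For a cycle with no dose change, "the total number of tablets taken in each cycle will be calculated as the number of days in the cycle where the doses were administered", doubled if the dose is divided.

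Results are summarised by regimen in the Safety Analysis Population, split at 80% ("The number and percentages of patients who are <80% compliant and" those at or above it), and listed by patient.

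The protocol directs departures from the Table 4 dose. In Section 5.6, "both agents will be held and restarted in parallel", and Table 7 prescribes interruptions and valganciclovir reductions. In Section 5.6.2, "Patients who develop an elevated creatinine while on study should have their dose of valganciclovir adjusted per Table 9".

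**The concern.** A compliance figure should say how much of what the patient was told to take was taken. Here the two parts of the ratio cover different things. The denominator reflects planned dosing over whole cycles, while the numerator reflects actual dosing over all time on drug. Dose lost because a patient obeyed the protocol then looks like poor adherence, and dose taken in a final partial cycle looks like extra adherence.

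Phase 1b is the part of the study that was run and will be reported (SAP 4.8). Its cohorts are planned at 3 to 6 patients, so one misclassified patient moves the below-80% row for a regimen by 1/6 = 17 to 1/3 = 33 percentage points.

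**Working it through.** The documents give no compliance figure to reproduce, so the check applies the written rule to illustrative patients. Hold lengths, stopping days and reductions are assumptions.

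**Inputs.** Nanatinostat tablets are 10 mg (Protocol 5.1.1) and valganciclovir tablets 450 mg (Protocol 5.2.1). Cycle 1 is 28 days and later cycles are 21 (Protocol 3.1.2). Level 9 is nanatinostat 20 mg + 20 mg every day (Table 4), so 4 tablets a day: 4 × 28 = 112 in Cycle 1 and 4 × 21 = 84 in each later cycle. Valganciclovir 900 mg once daily is 2 tablets a day: 56, then 42.

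**Formula.** Compliance = 100 × tablets taken / (Table 4 tablets summed over completed cycles). All patients in (a) to (c) take everything they were told to take, and real tablets are counted.

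(a) *Directed hold or reduction*
- Level 9 nanatinostat, 14-day hold wholly inside Cycle 2, two cycles completed: (112 + 7 × 4)/(112 + 84) = 140/196 = 71%.
- Valganciclovir 900 mg daily, halved for all of Cycles 2 to 5: (56 + 4 × 21)/(56 + 4 × 42) = 140/224 = 62.5%. The reduced dose, 450 mg once daily, appears nowhere in Table 4.

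Both fall under the 80% cut.

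(b) *Unfinished last cycle*
- Level 9 nanatinostat, stop on Day 14 of Cycle 3: (112 + 84 + 14 × 4)/196 = 252/196 = 129%.
- In general, with D days in completed cycles and d days in the partial cycle, the score passes 100% only if true adherence exceeds D/(D + d). For a stop on Day 10 of Cycle 2, 3 or 6 this is 28/38 = 73.7%, 49/59 = 83.1% or 112/122 = 91.8%.

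(c) *Stop in Cycle 1*
- Completed cycles = 0, so the denominator is 0 and the ratio is undefined. The patient has had at least one dose and is therefore in the Safety Analysis Population (SAP 4.2).

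(d) *The numerator as worded.* For an unchanged cycle it counts dosing days, doubled if divided, which is doses rather than tablets. A fully adherent patient in Cycle 1 then scores (28 × 2)/112 = 50% for nanatinostat at level 9 and (28 × 2)/224 = 25% at level 13. Only levels -1 and 6, with one tablet per dose, give 100%. Valganciclovir gives 28/56 = 50% at 900 mg once daily and 56/56 = 100% at 450 mg twice daily. If the same count is extended to the partial cycle, the 129% patient in (b) becomes (28 + 21 + 14) × 2 = 126/196 = 64%. Correcting the denominator alone is therefore not enough.

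**The case against.** The strongest case against is that little depends on this table and that the examples show the rule at its worst.

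- **Dose lost to toxicity is reported elsewhere.** SAP 4.6.1 to 4.6.3 give exposure duration, total dose, flagged interruptions over 14 days, adverse events leading to interruption or reduction, and DLTs. Protocol 7.4.2 assesses tolerability from adverse events leading to dose modification or discontinuation, and Protocol 5.5.2 does not list compliance among the RP2D considerations. This stands. A reader might infer that the definition undermines the RP2D; the documents do not support that.
- **The size depends on the scenario.** One more full cycle after the 14-day hold gives (280 − 56)/280 = 80.0%, which is not below the cut. A hold from Cycle 1 Day 22 costs only the 7 days inside the cycle (21/28 = 75%), because the next cycle waits until dosing resumes (Protocol 5.6, text after Table 8). For Grade 4 neutropenia or thrombocytopenia, Table 7 restores the valganciclovir dose once the lower one is tolerated for at least 4 weeks; four weeks of halving over five cycles gives (224 − 28)/224 = 87.5%. A longer reduction remains possible under other rules, such as Table 9. This stands as a limit on size.
- **A mid-cycle stop need not exceed 100%.** A patient with a 14-day hold in Cycle 1 who stops on Day 10 of Cycle 2 scores (14 + 10)/28 = 85.7%. The ratio is inflated in every such case but passes 100% only when the partial-cycle tablets outweigh the earlier shortfall.
- **The SAP refers to prescribed dosing in Table 4, not to the assigned level.** Nanatinostat reductions step to a lower dose level, so a step-down that Table 4 lists may already be covered. This stands for nanatinostat, but it does not reach valganciclovir doses missing from Table 4.
- **The SAP does not exclude Cycle 1 stoppers.** This is correct. They have no defined value, and what would be done with them is unstated.

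None of these points supplies a rule for in-cycle holds, for valganciclovir doses outside Table 4, or for partial cycles.

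**Conclusion.** The point holds within these limits. Followed literally, the denominator scores directed in-cycle holds and valganciclovir reductions to doses outside Table 4 as non-compliance, inflates the ratio for anyone who stops mid-cycle after Cycle 1, and is zero for anyone who stops in Cycle 1. Fully adherent patients can land at 71%, 62.5% or 129%, given the assumed hold, reduction and stopping day and a numerator that counts real tablets. How many Phase 1b patients are affected cannot be told from the documents.

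The consequence is a misleading descriptive table and listing. No endpoint, analysis set or named RP2D criterion changes. It should still be corrected before reporting, because the error lies in a stated rule and the repair is cheap.

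**What to change.** Amend SAP 4.5.2 as follows.

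1. Define expected tablets day by day from first to last dose, at the dose then prescribed: zero on directed hold days and scheduled off-days, and including the days of an unfinished last cycle. The patients in (a) and (b) then score 140/140, 140/140 and 252/252, all 100%. A Cycle 1 stopper becomes calculable; for example, 20 prescribed days all taken gives 20/20 = 100%.
2. Count tablets in the numerator as dose taken divided by tablet strength, in place of dosing days doubled if divided.
3. Separate directed holds from missed doses by using the recorded dose changes and interruptions on one side and the Missed/Dosing Error code on the other. Protocol 5.2.3 and 5.6 require prescribed doses, adjustments and interruptions in the eCRF but do not expressly require reasons, so the SAP should state how an interruption record is classified.
4. Report the ratio of tablets taken to the Table 4 dose over the same days as relative dose intensity, so that dose lost to toxicity stays visible.

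The cost is SAP wording, programming and one extra summary row.

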5.5. Dose Escalation Guidelines

5.5.1. Provisional Dose Levels

Table 4 describes the starting doses and the provisional dose levels of nanatinostat and valganciclovir (Phase 1b) and nanatinostat and valganciclovir with pembrolizumab (Phase 2 Dose Optimization and Phase 2 Expansion) to be evaluated. The actual dose levels will be determined based on available data following a discussion with Investigators during dose-escalation teleconferences. No intrapatient dose escalation will be permitted in the Phase 1b dose escalation.

Table 4: Phase 1b: Dose Levels – Nanatinostat and Valganciclovir

Dose Level	Nanatinostat Oral Dose on Days 1-4/Week	Valganciclovir Oral Dose Daily
-1	10 mg once daily	900 mg once daily
1	20 mg once daily	900 mg once daily
2	30 mg once daily	900 mg once daily
3	40 mg once daily	900 mg once daily
4	20 mg and 10 mg divided dose	900 mg once daily
5	20 mg twice daily	900 mg once daily
6	10 mg twice daily	900 mg twice daily × 21 days, then once daily
7	20 mg and 10 mg divided dose	900 mg twice daily × 21 days, then once daily
	Nanatinostat Oral Dose Twice Daily on Days 1-7/Week	Valganciclovir Oral Dose Twice Daily on Days 1-7/Week
8 ^a	20 mg and 10 mg divided dose	450 mg twice daily

9ª	20 mg and 20 mg divided dose 450 mg twice daily			
10 ^a	30 mg and 20 mg divided dose	450 mg twice daily		
11ª	30 mg and 30 mg divided dose	450 mg twice daily		
12ª	40 mg and 30 mg divided dose	450 mg twice daily		
13ª	40 mg and 40 mg divided dose	450 mg twice daily		

DLT = dose-limiting toxicity; RP2D = recommended Phase 2 dose

Guidelines for Dose Escalation 5.5.2.

During the DLT evaluation window of both phases of the study, patients who permanently discontinue study treatment prior to receiving 75% of the planned number of nanatinostat and valganciclovir doses or 2 pembrolizumab doses due to reasons other than study drug-related toxicity will not be considered evaluable for DLT and may be replaced.

Phase 1b

IND 154400

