The RP2D of nanatinostat in Phase 1b will be defined as the highest dose administered with standard daily doses of valganciclovir (900 mg once or 450 mg twice daily) for which <33% of patients experience a DLT (defined in Section 5.5.3) during the first treatment cycle (28 days) up to a maximum daily dose of 80 mg administered with food either as a single daily dose administered intermittently (Days 1 to 4 per week) or as a split dose twice daily administered continuously (Days 1 to 7 per week). In addition to toxicity, PK, antitumor activity, plus pharmacodynamic markers of disease response (plasma EBV DNA levels) will be considered in the final determination of the RP2D in consultation with the SMC. Dose escalation rules during Phase 1b are presented in Table 5.

Table 5: Phase 1b Dose Escalation Rules for Nanatinostat in Combination with Valganciclovir*

Dose level	Outcome	Action		
-1 Nanatinostat 10 mg daily,	If none of the first 3 patients experiences a DLT	Proceed to expansion cohorts.		
Days 1-4/wk	If 1 of 3 patients experiences a DLT	Enroll 3 more patients into dose level -1		
Valganciclovir 900 mg daily	If 1 of 6 patients experiences a DLT	Declare dose level -1 to be RP2D		
	If ≥2/6 patients experience a DLT	Convene safety review to discuss next steps.		
1 Starting dose	If none of the first 3 patients experiences a DLT	Proceed to dose level 2		
Nanatinostat 20 mg daily,	If 1 of 3 patients experiences a DLT	Enroll 3 more patients into dose level 1		
Days 1-4/wk	If 1 of 6 patients experiences a DLT	Proceed to dose level 2		
Valganciclovir 900 mg daily	If ≥2/6 patients experience a DLT	Decrease nanatinostat to dose level -1 and proceed.		
Nanatinostat 30 mg daily,	If none of the first 3 patients experiences a DLT	Proceed to dose level 3		
Days 1-4/wk	If 1 of 3 patients experiences a DLT	Enroll 3 more patients into dose level 2.		
Valganciclovir 900 mg daily	If 1 of 6 patients experiences a DLT	Proceed to dose level 3.		
	If ≥2/6 patients experience a DLT	Declare dose level 1 the RP2D.		

a: Dose levels 9, 11, and 13 are planned dose levels, while dose levels 8, 10, and 12 are planned provisional dose levels for stepping up or down based on the DLT profile to potentially better determine the RP2D. See Table 5 for further details.

Dose level	Outcome	Action			
3 Nanatinostat 40 mg daily,	If none of the first 3 patients experiences a DLT	Proceed to dose level 6.			

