The treatment period will begin on Cycle 1 Day 1. Cycle 1 will be 28 days; all subsequent cycles will be 21 days. Patients will be treated until unacceptable toxicity, death, progressive disease, treatment discontinuation at the discretion of the Investigator, or withdrawal of consent (maximum treatment duration with pembrolizumab is 24 months). Patients with first evidence of progressive disease and no clinical deterioration may continue study treatment until a repeat scan within 4 to 6 weeks confirms disease progression. To account for atypical disease response to immune therapy, Investigators are encouraged to follow immune-modified Response Evaluation Criteria in Solid Tumors (iRECIST) criteria (criteria based on RECIST v 1.1 for response and progressive disease, but adapted to account for the tumor response seen with immunotherapeutic drugs as described in Appendix 3 of the clinical study protocol) for treatment decision making, including confirmation of unconfirmed progressive disease with additional imaging.

Safety Follow-Up Period

Upon discontinuation of the protocol-specified treatments, patients will enter the Follow-up period. All patients must complete a safety follow-up assessment at 30 and 90 days after receiving their last dose of study drug. All AEs for patients treated with nanatinostat, valganciclovir, and pembrolizumab and only serious AEs (SAEs) for all other patients will be collected up to and including 90 days after the last dose of study treatment or until the start of a new antineoplastic therapy, whichever occurs first. The 90-day safety follow-up assessment may coincide with the first Long-Term Follow-Up visit.

Information related to concomitant medications used to treat AEs and any anti-neoplastic therapies taken following permanent discontinuation of study treatment will be collected for 90 days after the last dose of study treatment for all patients. If a new

antineoplastic treatment is initiated before the 30-day safety evaluation, safety follow-up will occur immediately before starting the new treatment. If a patient withdraws consent after the End of Treatment (EOT) visit, but prior to the 30-day safety evaluation, safety data should be collected on the patient up to the date of consent withdrawal.

Long-Term Follow-Up Visit

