4.6.1 Extent of Exposure

Extent of exposure to nanatinostat, valganciclovir, and pembrolizumab will be summarized for the Safety Analysis Population by dosing regimen. The duration of exposure for each drug will be presented in days and calculated as the date of last dose of study drug minus the date of first dose of study drug, plus one. Duration of exposure and total dose received will be summarized using descriptive statistics. Patients with dosing interruptions greater than 14 days will be flagged in associated patient data listings.

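### Programmed as written, SAP 4.5.2 divides administrations by tablets: a patient who misses nothing scores 25% to 67% on nanatinostat at 12 of the 14 dose levels and is reported as under 80% compliant

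*SAP*

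**What the plan says.** SAP 4.5.2 (Measurements of Treatment Compliance) sets compliance for nanatinostat and valganciclovir as 100 times tablets taken divided by tablets expected.

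- **Expected tablets.** These come from the doses in Protocol Table 4, "where nanatinostat and valganciclovir are dispensed in 10 mg and 450 mg tablets, respectively". They are worked out per cycle and "then multiplied by the number of cycles the patient completes".
- **Tablets taken.** For a cycle whose exposure record shows no change, interruption, delay or missed dose, the total is "calculated as the number of days in the cycle where the doses were administered (multiplied by two if a divided dose").
- **Reporting.** Compliance is summarized by dosing regimen in the Safety Analysis Population, with a split at 80% ("The number and percentages of patients who are <80% compliant" and those at or above 80%) and a by-patient listing.

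SAP 3.1 gives the cycle lengths: "Cycle 1 will be 28 days; all subsequent cycles will be 21 days". SAP 4.8 withdraws only the analyses specific to Phase 2, so the Phase 1b compliance output remains.

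**The concern.** Both sides of the ratio are called tablets, but only the denominator is in tablets. The rule for an unchanged cycle yields one unit per dosing day for a single dose and two for a divided dose, at any strength. Nothing else in 4.5.2 supplies the number of tablets per administration. Table 4 runs up to "40 mg and 40 mg divided dose", which is eight 10 mg tablets a day.

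If the sentence is programmed as it stands, patients with perfect dosing records will be reported as under 80% compliant at most dose levels. Differences between regimens will reflect tablets per administration and not adherence. A reader of the report could conclude that patients could not keep to the higher doses when they took all of them.

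A second, smaller point concerns the denominator. Computing a per-cycle count and multiplying by the number of cycles is not well defined when Cycle 1 is longer than the others.

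**Working it through.** The plan states no compliance figure, so there is none to reproduce. The check applies the SAP rule to a patient with no missed or changed doses.

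**Inputs.** Tablet strengths are 10 mg and 450 mg (Protocol 5.1.1 and 5.2.1; SAP 4.5.2). Doses and schedules are from Protocol Table 4. Dosing days in the 28-day Cycle 1 are 16 on the 4-days-per-week schedule and 28 on the 7-days-per-week schedule.

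**Formulas.**
- Taken (SAP rule) = dosing days × 1, or × 2 if the dose is divided.
- Expected = dosing days × daily mg / tablet strength.
- Score = taken / expected. Dosing days cancel, so for nanatinostat the score equals administrations per day divided by tablets per day.

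**Nanatinostat, Cycle 1**

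| Level | Dose (mg) | Tablets/day | Administrations/day | Taken / expected | Score |
|---|---|---|---|---|---|
| -1 | 10 | 1 | 1 | 16/16 | 100% |
| 1 | 20 | 2 | 1 | 16/32 | 50% |
| 2 | 30 | 3 | 1 | 16/48 | 33% |
| 3 | 40 | 4 | 1 | 16/64 | 25% |
| 4 | 20 + 10 | 3 | 2 | 32/48 | 67% |
| 5 | 20 + 20 | 4 | 2 | 32/64 | 50% |
| 6 | 10 + 10 | 2 | 2 | 32/32 | 100% |
| 7 | 20 + 10 | 3 | 2 | 32/48 | 67% |
| 8 | 20 + 10 | 3 | 2 | 56/84 | 67% |
| 9 | 20 + 20 | 4 | 2 | 56/112 | 50% |
| 10 | 30 + 20 | 5 | 2 | 56/140 | 40% |
| 11 | 30 + 30 | 6 | 2 | 56/168 | 33% |
| 12 | 40 + 30 | 7 | 2 | 56/196 | 29% |
| 13 | 40 + 40 | 8 | 2 | 56/224 | 25% |

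Twelve of 14 levels fall below 80%. A 21-day cycle gives the same ratios (Level 3: 12/48 = 25%; Level 9: 42/84 = 50%; Level 13: 42/168 = 25%), so the per-cycle score is also the patient's overall score.

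**Levels reached if no DLT occurs.** Protocol Table 5 then leads through Levels 1, 2, 3, 6, 7, 9, 11 and 13. Seven of these eight, all but Level 6, score below 80%.

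**Valganciclovir, Cycle 1**
- 900 mg once daily (Levels -1 to 5): 28/56 = 50%.
- 900 mg twice daily for 21 days, then once daily (Levels 6 and 7): (21×2 + 7)/(21×4 + 7×2) = 49/98 = 50%. Later cycles: 21/42 = 50%.
- 450 mg twice daily (Levels 8 to 13): 56/56 = 100%.

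**Reading of divided dose.** Every twice-daily regimen is counted here as divided, which favours the SAP. Table 4 labels nanatinostat Levels 5 and 6, and valganciclovir at Levels 6 to 13, as twice daily. If those were not doubled, the scores would be lower still: nanatinostat Level 5 16/64 = 25% and Level 6 16/32 = 50%; valganciclovir at Levels 8 to 13 28/56 = 50%.

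**Cycle length, with the numerator corrected.** For n completed cycles the true total is proportional to 28 + 21(n − 1) days.
- One 28-day count multiplied by n: n = 5 gives 112/140 = 80.0%; n = 6 gives 133/168 = 79.2%.
- One 21-day count multiplied by n: n = 5 gives 112/105 = 106.7%; n = 6 gives 133/126 = 105.6%.

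**After correction.** With taken = dosing days × prescribed tablets per day, Level 13 gives 224/224 = 100%. Every other level gives 100% on both drugs as well.

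**The case against.** The best defence is that the sentence is shorthand. The same section defines compliance in tablets, names the tablet strengths and draws on the exposure eCRF, and Protocol 5.9.3.1 has diaries collecting tablet counts. A programmer may well supply the missing factor, and 25% for patients with unchanged dosing would be conspicuous at the senior output review in SAP 3.5. That is plausible, but the text does not say it. Independent programming from the same sentence can reproduce the same error.

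It is also fair that 12 of 14 counts rows of a table and not patients. Some levels are alternative branches of Table 5, and the Table 4 footnote says that "Dose levels 9, 11, and 13 are planned dose levels, while dose levels 8, 10, and 12 are planned provisional dose levels". The documents do not show which levels enrolled or how many patients had every cycle unchanged, so the number affected is unknown. The point does not depend on that number: Level 1 is the starting dose, and a perfect record there scores 50% on both oral drugs.

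The cycle-length item is an ambiguity only. Summing over actual cycle lengths is the natural reading, and at five cycles the alternative gives exactly 80.0%, which is not below the cut-off.

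The objection on importance stands in part. The output is descriptive, no formal comparisons are planned, and SAP 4.6.1 reports dose separately: "Duration of exposure and total dose received will be summarized using descriptive statistics". This limits the harm but does not make the compliance table right.

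**Conclusion.** The concern holds. On the text as written, a fully compliant patient scores 25% to 67% on nanatinostat at 12 of 14 Table 4 levels (7 of 8 on the no-DLT path) and 50% on valganciclovir at 8 of 14 (Levels -1 to 7), and is placed in the under-80% category for that drug. Agreement occurs only where each administration is one tablet: nanatinostat Levels -1 and 6, and valganciclovir Levels 8 to 13.

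This rests on three conditions: the rule is programmed literally, every cycle is recorded as unchanged, and twice-daily dosing counts as divided. The SAP does not spell out the numerator for cycles with changed or missed doses, so no figure is claimed for them.

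The damage is confined to the Phase 1b compliance summary, its 80% split and the listing. Compliance is not an input to DLT assessment, RP2D selection or efficacy. It should be corrected before the output is programmed, but it does not threaten the study's main conclusions.

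**What to change.** In SAP 4.5.2:

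1. For a cycle with no change to dose, set tablets taken to dosing days × prescribed tablets per day (daily mg / 10 for nanatinostat, daily mg / 450 for valganciclovir), using the dose in force on each day so that the step from twice to once daily at Levels 6 and 7 is handled. Alternatively, define compliance as mg taken over mg prescribed.
2. State that expected tablets are summed over the cycles completed, 28 days for Cycle 1 and 21 days for each later cycle.
3. Say that cycles with changed or missed doses are also counted in tablets. The convention that a date recorded as missed or in error counts as undosed can stay.

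The cost is a few sentences of SAP text and the matching programming. No new data are needed.
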